This material is the property of the Feinstein Institute for Medical Research, North-Shore-LIJ Health System. Do not disclose or use except as authorized in writing by the study sponsor

Page iii

8.3.1	1 Study Sponsor Notification by Investigator	
8.3.2		
8.3.3	3 FDA Notification by Sponsor	
8.4	UNBLINDING PROCEDURES	
8.5	STOPPING RULES	
8.6	MEDICAL MONITORING	
8.6.1	I Independent Data and Safety Monitoring Board	23
9 DAT	FA HANDLING AND RECORD KEEPING	23
9.1	CONFIDENTIALITY	
9.2	SOURCE DOCUMENTS	
9.3	CASE REPORT FORMS	
9.4	RECORDS RETENTION	
10 STU	JDY MONITORING, AUDITING, AND INSPECTING	24
10 510		•••••••••••••••••••••••••••••••••••••••
10 510	STUDY MONITORING PLAN	
10.1 10.2	STUDY MONITORING PLAN	
10.1 10.2	STUDY MONITORING PLAN	24 24 25
10.1 10.2 11 ETH	STUDY MONITORING PLAN Auditing and Inspecting	
10.1 10.2 11 ETH 11.1 11.2	Study Monitoring Plan Auditing and Inspecting HICAL CONSIDERATIONS Study Risks/Discomforts	24 24 25 25 25
10.1 10.2 11 ETH 11.1 11.2	STUDY MONITORING PLAN AUDITING AND INSPECTING	24 24 25 25 25 25 26
10.1 10.2 11 ETH 11.1 11.2 12 STU	STUDY MONITORING PLAN AUDITING AND INSPECTING	24 24 25 25 25 25 26
10.1 10.2 11 ETH 11.1 11.2 12 STU 12.1 12.2	STUDY MONITORING PLAN AUDITING AND INSPECTING	24 24 25 25 25 25 26 26

List of Abbreviations

AIED: Autoimmune Inner Ear Disease

ANC: Absolute Neutrophil Count

CBC: Complete Blood Count with differential

dB: Decibel

IL-1β: Interleukin-1 beta

IL1R2: Interleukin-1 Receptor type II

PBMC: Peripheral Blood Immune Cells

PTA: Pure Tone Average, here to include the average of 250, 500 1000, 2000 and 4000 Hertz SMA-7: Serum Metabolic Assay-7: Includes determination of blood sodium, potassium, glucose, and creatinine

SNHL: Sensorineural Hearing Loss

SSNHL: Sudden Sensorineural Hearing Loss

TNF-α: Tumor Necrosis Factor-alpha

Study Summary

Title	A phase I/II, open-label study of the effects of anakinra in corticosteroid-resistant subjects with autoimmune inner ear disease	
Short Title	A phase I/II trial of anakinra in AIED	
Phase	I/II	
Methodology	An open-label, phase I/II trial	
Study Duration	60 months	
Study Center(s)	North Shore-LIJ Health System	
Objectives	To determine if anakinra treatment results in hearing improvement in corticosteroid resistant individuals with Autoimmune Inner Ear Disease	
Number of Subjects	38	
Diagnosis and Main Inclusion Criteria	Autoimmune Inner Ear Disease. Patients to be included are those that failed to improve their hearing in response to a 28-30 day course of corticosteroid therapy.	
Study Product, Dose, Route, Regimen	Anakinra: 100 mg/day administered daily by subcutaneous injection.	
Duration of administration	Administration is to occur daily for 84-day duration.	
Reference therapy	None.	
Statistical Methodology	A simon 2-stage design: in year 1 a minimum efficacy of 2 or more positive responses of 10 total evaluable events (patients): if this milestone is met, a response rate of 30% or greater would warrant progression to a phase II study.	

1 Introduction

This document is a protocol for a human research study. This study is to be conducted according to US and international standards of Good Clinical Practice (FDA Title 21 part 312 and International Conference on Harmonization guidelines), applicable government regulations and Institutional research policies and procedures.

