7.1 Sample Size Determination & Statistical Methods

Corticosteroid resistant AIED patients currently have no therapeutic alternatives available to them. These patients that failed initial corticosteroid therapy are not expected to demonstrate a placebo effect, as they have already undergone 2 serial audiograms that demonstrated a <5dB PTA improvement in hearing for trial inclusion. A Simon 2-stage "optimal" design will be used to test the null hypothesis that the true objective response rate (RR) is 10% or less (which would not be clinically meaningful) versus the alternative hypothesis that the true response rate is 30% or greater. With a significance level of 0.05 and a power of 0.80, a maximum total of 29 evaluable patients will be required to assess the objective response rate. Ten (10) evaluable patients will be enrolled in Stage 1(R21 phase). If 1 or fewer objective responses are observed in the first 10 evaluable patients, then the trial will be terminated (do not proceed to R33). Primary milestone: If 2 or more objective responses (improvement in the PTA \geq 5dB) are observed in the first 10 patients (20%), we will proceed to the R33 phase.

If the RR is 10% or less, then the expected sample size for the trial is 15 patients and the probability of early termination at the end of the R21 phase (stage 1) is 74%. Overall, a total of approximately 38 patients may be enrolled in this R21/R33 study to ensure that the specified numbers of evaluable patients are available for analysis at each stage.

Given that anakinra may cause injection site reactions, it is possible that some patients will prematurely self-terminate the study. In order to appropriately evaluate the results, 29 patients would need to complete the 84-day course of anakinra. Overall, a total of 38 patients may be enrolled in this study to ensure that the specified numbers of evaluable patients are available for analysis at each stage.

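### The Summary's end-of-trial criterion, a response rate of 30% or greater, does not match the final boundary of 6 of 29 that section 7.1's design implies but does not print

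*Protocol*

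**What the plan says.** Protocol, section 7.1 (Sample Size Determination & Statistical Methods) names a Simon two-stage optimal design. It is to "test the null hypothesis that the true objective response rate (RR) is 10% or less" "versus the alternative hypothesis that the true response rate is 30% or greater". The size is given as follows: "With a significance level of 0.05 and a power of 0.80, a maximum total of 29 evaluable patients will be required". For the first stage, "Ten (10) evaluable patients will be enrolled in Stage 1", and "If 1 or fewer objective responses are observed in the first 10 evaluable patients, then the trial will be terminated". The section adds that under the null the expected sample size is 15 and the probability of early termination is 74%. It does not print the number of responders of 29 at which the null is rejected.

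The Study Summary (row Statistical Methodology) repeats the stage 1 milestone of 2 or more responders of 10 and continues: "if this milestone is met, a response rate of 30% or greater would warrant progression to a phase II study". No other end-of-trial criterion appears in the protocol.

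**The concern.** In section 7.1, 30% is a true response rate: the value at which the trial is meant to have 80% power. In the Summary the same 30% appears as the response rate that triggers the next step. These are different things. A two-stage test of 10% against 30% rejects the null at an observed rate well below 30%. If the alternative itself is used as the cut-off, a treatment whose true rate is exactly 30% falls short about half the time.

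The trial is single-arm and open-label, and its main product is a go or no-go decision. With two possible final thresholds in one document, a result of 6, 7 or 8 responders of 29 could be called a success or a failure after the data are seen. Section 6 discloses that the sponsor-investigator and the institute hold a use patent for this type of therapy, which is a further reason to fix the threshold in advance.

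**Working it through.** **Inputs.** All come from section 7.1, except the final criterion, which is from the Study Summary.
- Null rate 0.10, alternative rate 0.30.
- Stage 1: 10 patients, stop at 1 or fewer responders.
- Maximum 29 evaluable patients, so 19 in stage 2.
- Alpha 0.05, power 0.80.
- Final criterion in the Summary: response rate of 30% or greater.

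**Formula.** Let X1 be the responders among the first 10 and X2 those among the next 19, both binomial with rate p. For a final boundary of r responders,

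P(success | p) = sum over x = 2 to 10 of P(X1 = x) × P(X2 ≥ r − x).

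This is the type I error at p = 0.10 and the power at p = 0.30.

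**Step 1: reproduce the plan's own figures.**
- Early termination at p = 0.10: 0.9^10 + 10 × 0.1 × 0.9^9 = 0.3487 + 0.3874 = 0.736. The plan states 74%.
- Expected sample size: 10 + (1 − 0.736) × 19 = 15.0. The plan states 15.
- A search for the optimal design at these rates, alpha and power returns 10 patients in stage 1, stop at 1 or fewer, 29 in total, and success at 6 or more of 29, with alpha 0.0471 and power 0.8051.

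The stated design is therefore reproduced in full.

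**Step 2: find the count that the Summary's criterion needs.** 0.30 × 29 = 8.7. 8/29 = 27.6% falls short and 9/29 = 31.0% qualifies, so 9 responders are needed. The boundary in step 1 is 6/29 = 20.7%.

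**Step 3: compare final boundaries after at least 2 of the first 10.**

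| Responders needed of 29 | Observed rate | Type I error (p = 0.10) | Power (p = 0.30) |
|---|---|---|---|
| 5 | 17.2% | 0.102 | 0.837 |
| 6 | 20.7% | 0.047 | 0.805 |
| 7 | 24.1% | 0.018 | 0.739 |
| 8 | 27.6% | 0.005 | 0.633 |
| 9 | 31.0% | 0.0014 | 0.497 |

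Only 6 of 29 keeps alpha at or below 0.05 and power at or above 0.80.

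**Step 4: size of the disputed zone.** At p = 0.30, the probability of passing stage 1 and ending with 6, 7 or 8 of 29 is 0.805 − 0.497 = 0.308.

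**Step 5: true rate needed under the 9-of-29 rule.** Power is 0.709 at a true rate of 35% and 0.859 at 40%. It reaches 0.80 at about 38%.

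**Step 6: if fewer than 29 are evaluable.** With the boundary kept at 6, power at p = 0.30 is 0.793 for 28 patients and 0.779 for 27. The type I error is 0.042 and 0.037, so it stays below 0.05.

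**The case against.** Three arguments stand against the point.

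**Section 7.1 contains no error.** This is right. A reader might infer that the 80% is miscalculated, and the documents do not support that: every figure in the section reproduces. The stated design also fixes the final boundary uniquely at 6 of 29. That the count is not printed would not be a fault on its own, because a statistical analysis plan commonly supplies it.

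**The Summary sentence may not be a test rule.** It could be a compressed statement of the alternative hypothesis, since it uses the same figure and does not say observed, 9 or 29. Or it could be a development bar, deliberately stricter than statistical significance, to which the 80% power claim does not apply. Both readings are reasonable. For this reason the stronger inference, that the trial as written fails half the time when the drug works as hoped, goes too far. It holds only if the 30% is applied to the observed rate as the success rule.

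**Little depends on it in practice.** The stage 1 rule is the same in both places, and sample size, data collection and interim conduct are unaffected. This also stands.

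These arguments do not remove the conflict. The Summary sentence follows a milestone expressed as an observed count, and it attaches an action to a response rate. A true rate is never observed and cannot trigger an action. Section 7.1 writes of the true rate where it means that, and the Summary does not. If only the alternative hypothesis was meant, the one end-of-trial criterion a reader can apply is misleading. If a separate development bar was meant, its properties are not given.

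**Conclusion.** The point holds as an inconsistency between the Study Summary and section 7.1, and not as an error of calculation. Section 7.1's alpha of 0.05 and power of 0.80 belong to a final boundary of at least 6 of 29. The Summary's 30%, read as an observed cut-off, means at least 9 of 29, with alpha 0.0014 and power 0.497 at a true rate of 30%. Results of 6 to 8 of 29 pass one and fail the other.

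This rests on three assumptions: that the 30% refers to the observed rate, that exactly 29 patients are evaluable, and that the stage 1 rule is followed as written. The first is the natural reading but not the only one, so the sponsor should say which is meant. A statistical analysis plan that is not shown might print the boundary. If it gave 6 of 29, the Summary would still need to be brought into line with it.

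**What to change.** State in section 7.1 and in the Study Summary that the null hypothesis (response rate 10% or less) is rejected if at least 2 of the first 10 and at least 6 of 29 evaluable patients respond. Say in the Summary that 30% is the alternative hypothesis.

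If the sponsor does intend an observed 30% as the threshold for going on, it can stay, labelled as a separate development criterion. The text should then say that it needs 9 of 29 and has a power of about 0.50 at a true rate of 30% and an alpha of about 0.001.

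Base the test on the first 29 evaluable patients, the stated maximum. The 38 in section 7.1 is an enrolment allowance to secure those 29, so no set of cut-offs for larger totals is needed. If fewer than 29 are evaluable, keep 6 responders as the boundary and report the lower power (0.793 at 28, 0.779 at 27).

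The cost is one or two sentences in each place. No extra patients, visits or data are needed.

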1.1 Background

The mechanisms that control corticosteroid responsive sensorineural hearing loss remain enigmatic. For patients that experience an acute, sensorineural decline in hearing, timely corticosteroid administration may result in preservation of some or all of the hearing. Factors that contribute to these responses have not been fully characterized, but include audiometric configuration, degree of hearing loss, presence of circulating auto-antibodies to antigens such as the 68kD protein(1) and CTCL2(2), absence of vertigo and absence of retrocochlear pathology. Interestingly, the influence of cytokine microenvironment has not been investigated to any great degree in this disorder, largely, because the events in the cochlea may not be reflected in the peripheral blood immune cells (PBMC). Potentially reversible sensorineural hearing loss (SNHL) can be divided into several sub-groups: Autoimmune Inner Ear Disease (AIED), sudden SNHL (SSNHL) and Meniere's Disease. SSNHL is usually a unilateral, isolated event. Patients with AIED usually experience multiple episodes of rapid hearing loss either concurrently or sequentially in both ears. Of those with AIED, up to 30% may have a systemic autoimmune disease (3). Some patients with SSNHL are considered to have an autoimmune etiology for their disease (4), although the majority of these patients have either a viral trigger of their disease. Estimates of disease prevalence for SSNHL are that there are 15,000 new cases reported per year. For AIED, it is estimated that there is only 1 case per 1,000 cases of all SNHL. However, characterization of the mechanisms involved in steroid responsive hearing loss has been difficult because of limited access to the human cochlea. Moreover, although a number of antibodies to autoantigens have been found in patients with AIED (5), no single diagnostic biomarker has been identified (6). Some physicians have used initial responsiveness to glucocorticoids as a hallmark of this poorly defined clinical disorder (3, 7-9). The durability of continued corticosteroid responsiveness for multiple declines in hearing is limited. Of the 70% (10) of patients who are initially steroid responsive, only 14% remain so after 34 months (10). However, the mechanism(s) that govern steroid resistance in these patients is unknown. Treatment options for those that fail corticosteroids are ineffectual. Methotrexate has been shown to be no better than placebo in a large clinical trial. Similarly, in clinical trials of anti-TNF- α therapy have also shown no benefit (11, 12).

Precedent for the causal role of Interleukin-1 β (IL-1 β) involvement in hearing loss exists. Macrophage ingress into the cochlea has been demonstrated in animal models of acousticinduced trauma (13). In this model, IL-1 β is expressed by macrophages, and dictated many of the later adaptive immune responses (14). Administration of methylprednisolone in the acoustic injury trauma model was capable of preventing cochlear hair cell loss, however, only if administered prior to, or immediately following injury (15). IL-1 β expression was also observed in an animal model of AIED (16). In this model, LPS was required in addition to antigen re-exposure to initiate cochlear Interleukin-1 β (IL-1 β) expression, leukocyte ingress into the cochlea and hearing loss (23). Sensorineural hearing loss has been observed in the

autoinflammatory syndromes NOMID and Muckle-Wells whose hallmarks are IL-1 β dysregulation. IL-1 β blockade may represent an alternative method to clinically restore hearing in patients who do not respond to corticosteroid therapy. IL-1 β blockade with anakinra has already been shown to reverse sensorineural hearing loss in Muckle-Wells syndrome (**17**). Unlike these autoinflammatory disorders, AIED is likely a true autoimmune disease where cochlin has been identified as a good candidate antigen, an animal model based on cochlin reactivity has been established (**18**), and cochlin specific T-cells have been identified in patients with clinical disease (**19**).

1.2 Investigational Agent

DESCRIPTION

Anakinra (Kineret) is a recombinant, nonglycosylated form of the human interleukin-1 receptor antagonist (IL-1Ra). Anakinra differs from native human IL-1Ra in that it has the addition of a single methionine residue at its amino terminus. Anakinra consists of 153 amino acids and has a molecular weight of 17.3 kilodaltons. It is produced by recombinant DNA technology using an E coli bacterial expression system.

Anakinra is supplied in single use prefilled glass syringes with 27 gauge needles as a sterile, clear, colorless-to-white, preservative-free solution for daily subcutaneous (SC) administration. The solution may contain trace amounts of small, translucent-to-white amorphous proteinaceous particles. Each prefilled glass syringe contains: 0.67 mL (100 mg) of anakinra in a solution (pH 6.5) containing sodium citrate (1.29 mg), sodium chloride (5.48 mg), disodium EDTA (0.12 mg), and polysorbate 80 (0.70 mg) in Water for Injection, USP.

CLINICAL PHARMACOLOGY

Anakinra blocks the biologic activity of IL-1 by competitively inhibiting IL-1 binding to the interleukin-1 type I receptor (IL-1RI), which is expressed in a wide variety of tissues and organs.

1 IL-1 production is induced in response to inflammatory stimuli and mediates various physiologic responses including inflammatory and immunological responses. IL-1 has a broad range of activities including cartilage degradation by its induction of the rapid loss of proteoglycans, as well as stimulation of bone resorption. 2 The levels of the naturally occurring IL-1Ra in synovium and synovial fluid from rheumatoid arthritis (RA) patients are not sufficient to compete with the elevated amount of locally produced IL-1.

Pharmacokinetics

The absolute bioavailability of Anakinra after a 70 mg SC bolus injection in healthy subjects (n = 11) is 95%. In subjects with RA, maximum plasma concentrations of Anakinra occurred 3 to 7 hours after SC administration of Anakinra at clinically relevant doses (1 to 2 mg/kg; n = 18); the terminal half-life ranged from 4 to 6 hours. In RA patients, no unexpected accumulation of Anakinra was observed after daily SC doses for up to 24 weeks.

The influence of demographic covariates on the pharmacokinetics of Anakinra was studied using population pharmacokinetic analysis encompassing 341 patients receiving daily SC injection of Anakinra at doses of 30, 75, and 150 mg for up to 24 weeks. The estimated Anakinra clearance

increased with increasing creatinine clearance and body weight. After adjusting for creatinine clearance and body weight, gender and age were not significant factors for mean plasma clearance (from PDR.net).

1.3 Preclinical Data

Patients with AIED are treated with corticosteroids, however, of those treated; only half respond, and fewer respond over time. Factors that influence steroid responsiveness include low basal expression of Interleukin-1 Receptor type II (IL1R2) that is strongly induced by in vitro treatment of Peripheral Blood Immune Cells (PBMC) by dexamethasone. Pre-treatment evaluation of IL1R2 expression patterns correlated with clinical response to corticosteroids (p<0.0001) (20). Patients that are corticosteroid resistant demonstrate high basal expression levels of IL1R2, and cannot be further induced by *in vitro* corticosteroid treatment of PBMC.

[figure not shown]
We postulated that corticosteroid resistant individuals had higher circulating levels of IL-1ß than corticosteroid responsive individuals. Indeed, in a study of 43 patients, steroid nonresponders demonstrated significantly higher plasma levels of IL-1ß than corticosteroid responders (67.6 vs. 5.1 units (p=0.0005, two tailed t-test) figure 1A). Given the correlation of plasma IL-1ß expression with clinical steroid response, we asked whether the PBMC from steroid responders and non-responders have altered cytokine production or release in response to anakinra. PBMC from a subset of pre-treatment clinical corticosteroid responders and pretreatment non-responders were cultured with anakinra, and mRNA from these PBMC was assessed for IL-1ß expression by Q-RT-PCR. In all responders, dexamethasone inhibited mRNA expression of IL-1 β , whereas in non-responders, the effect of dexamethasone on IL-1 β was variable, with no clear inhibitory pattern seen (figure 1B). When the culture supernatant was examined, IL-1ß was reduced, as expected, in the dexamethasone-treated PBMC of corticosteroid responders. Notably, however, in corticosteroid non-responders, dexamethasone treatment caused a paradoxical increase in IL-1ß mRNA transcription, and dexamethasone also failed to prevent IL-1 β release, with high levels of IL-1 β detected in the conditioned media. This failure to repress IL-1ß production and release would permit the initiation of a pro-inflammatory microenvironment that precludes a steroid response.

Figure Legend:

1A: Plasma from 43 corticosteroid patients. Results were stratified to corticosteroid responsiveness as described below. Results are from 26 responders and 17 non-responders. IL-1 β levels are statistically significantly elevated in corticosteroid non-responders, p=0.0005 (Mann-Whitney two tailed test).

1B: Pre-treatment PBMC from a minimum of 6 responders and 6 non-responders. PBMC were isolated and plated at a density of 1×10^6 cells/ml. Cells were cultured with either dexamethasone or anakinra and compared with unstimulated, cultured PBMC. RNA from these PBMC were analyzed by quantitative real time PCR for transcription of IL-1 β . The mean fold change (+ SEM) observed in response to drug relative to the unstimulated PBMC level was calculated. 1C: IL-1 β released into the cultured supernatant was measured by ELISA for the stimulus conditions and again compared to unstimulated, cultured PBMC.

1A

CONFIDENTIAL This material is the property of the Feinstein Institute for Medical Research, North-Shore-LIJ Health System. Do not disclose or use except as authorized in writing by the study sponsor

1.4 Clinical Data to Date

Clinical data available for the safety and efficacy has been established in clinical trials of rheumatoid arthritis patients. The safety and efficacy of Anakinra have been evaluated in three randomized, double-blind, placebo-controlled trials of 1790 patients \geq 18 years of age with active rheumatoid arthritis (RA). An additional fourth study was conducted to assess safety. In the efficacy trials, Anakinra was studied in combination with other disease-modifying antirheumatic drugs (DMARDs) other than Tumor Necrosis Factor (TNF) blocking agents (studies 1 and 2) or as a monotherapy (study 3).

Study 1 involved 899 patients with active RA who had been on a stable dose of methotrexate (MTX) (10 to 25 mg/week) for at least 8 weeks. All patients had at least 6 swollen/painful and 9 tender joints and either a C-reactive protein (CRP) of \geq 1.5 mg/dL or an erythrocyte sedimentation rate (ESR) of \geq 28 mm/hr. Patients were randomized to Anakinra or placebo in addition to their stable doses of MTX. The first 501 patients were evaluated for signs and symptoms of active RA. The total 899 patients were evaluated for progression of structural damage.

Study 2 evaluated 419 patients with active RA who had received MTX for at least 6 months including a stable dose (15 to 25 mg/week) for at least 3 consecutive months prior to enrollment. Patients were randomized to receive placebo or one of five doses of Anakinra SC daily for 12 to 24 weeks in addition to their stable doses of MTX.

Study 3 evaluated 472 patients with active RA and had similar inclusion criteria to study 1 except that these patients had received no DMARD for the previous 6 weeks or during the study.7 Patients were randomized to receive either Anakinra or placebo. Patients were DMARD-naïve or had failed no more than 3 DMARDs.

Study 4 was a placebo-controlled, randomized trial designed to assess the safety of Anakinra in 1414 patients receiving a variety of concurrent medications for their RA including some DMARD therapies, as well as patients who were DMARD-free. The TNF blocking agents etanercept and infliximab were specifically excluded. Concurrent DMARDs included MTX, sulfasalazine, hydroxychloroquine, gold, penicillamine, leflunomide, and azathioprine. Unlike studies 1, 2 and 3, patients predisposed to infection due to a history of underlying disease such as pneumonia, asthma, controlled diabetes, and chronic obstructive pulmonary disease (COPD) were also enrolled (see ADVERSE REACTIONS: Infections).

In studies 1, 2 and 3, the improvement in signs and symptoms of RA was assessed using the American College of Rheumatology (ACR) response criteria (ACR20, ACR50, ACR70). In these studies, patients treated with Anakinra were more likely to achieve an ACR20 or higher magnitude of response (ACR50 and ACR70) than patients treated with placebo (Table 1). The treatment response rates did not differ based on gender or ethnic group. The results of the ACR component scores in study 1 are shown in Table 2.

Most clinical responses, both in patients receiving placebo and patients receiving Anakinra, occurred within 12 weeks of enrollment.

Study 1 (Patients on MTX)			Study 3 (No DMARDs)				
		Kineret		Kineret			
	Placebo (n =	100 mg/day (n =	Placebo (n =	75 mg/day (n =	150 mg/day (n =		
Response	251)	250)	119)	115)	115)		
a p < 0.05,	Kineret versus	placebo					
b p < 0.01,	Kineret versus	placebo					
c p < 0.001	l, Kineret versu	s placebo					
ACR20							
Month 3	24%	34%a	23%	33%	33%		
Month 6	22%	38%c	27%	34%	43%a		
ACR50							
Month 3	6%	13%b	5%	10%	8%		
Month 6	8%	17%b	8%	11%	19%a		
ACR70							
Month 3	0%	3%a	0%	0%	0%		
Month 6	2%	6%a	1%	1%	1%		

Table 1: Percent of Patients with ACR Responses in Studies 1 and 3

Table 2: Median ACR Component Scores in Study 1

	Placebo/MTX	(n = 251)	Kineret/MTX 1 25		
Parameter (median)	Baseline	Month 6	Baseline	Month 6	
 a Health Assessment Questionnaire; 0 = best, 3 = worst; includes eight categories: dressing and grooming, arising, eating, walking, hygiene, reach, grip, and activities. b Visual analog scale; 0 = best, 100 = worst c Scale 0 to 68 					
d Scale 0 to 66					
Patient Reported Outcomes					
Disability index	1.38	1.13	1.38	1.00	
Patient global assessment b	51.0	41.0	51.0	29.0	
Pain b	56.0	44.0	63.0	34.0	
Objective Measures					
ESR (mm/hr)	35.0	32.0	36.0	19.0	
CRP (mg/dL)	2.2	1.6	2.2	0.5	
Physician's Assessments					
Tender/painful joints	20.0	11.0	23.0	9.0	
Physician global assessment	59.0	31.0	59.0	26.0	
Swollen joints	18.0	10.5	17.0	9.0	

A 24-week study was conducted in 242 patients with active RA on background methotrexate who were randomized to receive either etanercept alone or the combination of Anakinra and

etanercept. The ACR50 response rate was 31% for patients treated with the combination of Anakinra and etanercept and 41% for patients treated with etanercept alone, indicating no added clinical benefit of the combination over etanercept alone. Serious infections were increased with the combination compared to etanercept alone.

In study 1, the effect of Anakinra on the progression of structural damage was assessed by measuring the change from baseline at month 12 in the Total Modified Sharp Score (TSS) and its subcomponents, erosion score, and joint space narrowing (JSN) score.8 Radiographs of hands/wrists and forefeet were obtained at baseline, 6 months and 12 months and scored by readers who were unaware of treatment group. A difference between placebo and Anakinra for change in TSS, erosion score (ES) and JSN score was observed at 6 months and at 12 months (Table 3).

Table 3: Mean Radiographic Changes Over 12 Months in Study 1

Placebo/MTX ($N = 450$)		Kineret 100 mg/day/MTX (N = 449)		Placebo/MTX vs. Kineret/MTX			
	Dogolino	Change at Month 12	Dogolino	Change at Month		p-	
	BaselineMonth 12Baseline12Interval*value*** Differences and 95% confidence intervals for the differences in change scores between						
Placebo/MTX and Kineret/MTX							
** Based on Wilcoxon rank-sum test							
TSS	52	2.6	50	1.7	0.9 [0.3, 1.6]	< 0.001	
Erosion	28	1.6	25	1.1	0.5 [0.1, 1.0]	0.024	
JSN	24	1.1	25	0.7	0.4 [0.1, 0.7]	< 0.001	

The disability index of the Health Assessment Questionnaire (HAQ) was administered monthly for the first six months and quarterly thereafter during study 1. Health outcomes were assessed by the Short Form-36 (SF-36) questionnaire. The 1-year data on HAQ in study 1 showed more improvement with Anakinra than placebo. The physical component summary (PCS) score of the SF-36 also showed more improvement with Anakinra than placebo but not the mental component summary (MCS). *All data from this section is from PDR.net, search Kineret, PDR Full Label, Manufacturer, Biovitrum.*

